## 4. STUDY POPULATION

We intend to enroll eighteen (6 female, 12 male) completers into this study. These individuals must be English-speaking, English-reading volunteers 18-55 years of age of varying ethnic backgrounds. Enrollment in this study will occur between January 1, 2015 and December 31, 2017. Volunteers will be required to provide legal proof of age.

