## 7. RESEARCH PROCEDURES

*General Procedures.* Volunteers that meet the inclusion criteria will participate as inpatients at the University of Kentucky Clinical Research Unit (CRU). Volunteers will be discharged upon completion of the entire protocol.

This experiment will require each volunteer to participate for 33 days. Sessions will be conducted as outlined in Table 1 (see below). Please note three important points relating to the table below: 1) The sequence of maintenance conditions and the cocaine and d-amphetamine maintenance doses are illustrative. The order of d-amphetamine SR maintenance will be random, with one exception. The lower active d-amphetamine SR maintenance condition will be tested prior to the higher active condition. The cocaine dose order available for self-administration will be randomly determined. 2) Please also note that participation will require a minimum of three additional sessions to avoid experimental testing on weekends. More than three additional sessions might be required depending on the day of the week that a subject is admitted to the unit. 3) If subjects leave the protocol for a reason unrelated to study procedures (e.g., a family emergency or dental problems), they may be re-admitted with physician approval to complete the remainder of the protocol, picking up with the next maintenance condition after the last one completed. Thus, they may not complete the protocol over one approximately 33-day admission.

To confirm equivalent maintenance dosing across species, blood will be drawn from the indwelling catheter used for drug administration on the first and last of the four experimental sessions during each maintenance phase in order to determine plasma levels of d-amphetamine. If necessary due to trouble with the catheter, the blood sample will be drawn directly with a needle and syringe. Samples will be processed and stored by the BAL/CCTS and then shipped to the ARUP laboratories at the University of Utah for analysis using liquid chromatography / mass spectroscopy (LC/MS). Samples submitted for analysis will not contain any PHI.

Day	Table 1
1	Admission to the CRU and practice session.
2	Medical Safety Session. Start d-amphetamine maintenance in PM.
3-11	d-Amphetamine SR maintenance (30 mg daily). Oral dose administered twice daily (0700 and 1900 h) in escalating fashion, based on clinical dosing recommendations, up to target daily dose (i.e., doses 1-3 = 5 mg, doses 4&5 = 10 mg, remaining doses = 15 mg).

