8-11	Self-administration sessions. Subjects complete 1 sample and 9 choice trials to receive cocaine (0, 3, 10 and 30 mg/70 kg) or money (\$6.00) by responding on the concurrent PR schedule.
12-20	d-Amphetamine SR maintenance (placebo; 0 mg administered twice daily).
17-20	Self-administration sessions. Details are the same as Days 10-13.
21-29	d-Amphetamine SR maintenance (60 mg daily). Oral dose administered twice daily (0700 and 1900 h) in escalating fashion up to target daily dose (i.e., doses 1-3 = 5 mg, doses 4&5 = 10 mg, doses 6&7 = 20 mg, remaining doses = 30 mg).
26-29	Self-administration sessions. Details are the same as Days 10-13.
30	Discharge from the CRU.

During their participation in the research protocol, volunteers will not be allowed to leave the CRU, nor will visitors be allowed. Research volunteers will be allowed to make local telephone calls. After completing the

research protocol, interested volunteers will be offered a referral to an appropriate drug abuse treatment program.

All volunteers will provide urine and expired air samples daily during study participation once experimental sessions have been initiated. The presence of non-nicotine, non-cannabinoid drugs of abuse or alcohol not administered experimentally in the research protocol will result in immediate termination from the research study.

This experiment will consist of 12 experimental sessions across approximately 33 days and conducted according to the timeline in Table 1 (see above). On the day of admission, volunteers will be allowed to acclimate to the CRU. During this time, volunteers will be maintained on a caffeine-free diet, receive instructions concerning the details of the daily research procedures and general rules of the inpatient research unit and complete a "practice" session to familiarize them with the experimental routine and tasks. The practice session will follow the session timeline with the exception that no drug or response-contingent money will be available and no maintenance dose will be administered. On the day after the practice session, subjects will participate in a medical safety session in which they will receive each of the doses IV cocaine that will be available in subsequent sessions (i.e., 1 infusion of 0, 3, 10 and 30 mg/70kg cocaine) administered in ascending order and separated by 30-min intervals; subjects exceeding the predetermined cardiovascular parameters will be excluded from further participation.

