d-Amphetamine SR doses will be prepared using commercially available tablets and cornstarch placed into size 0 opaque capsules. Placebo capsules will contain only cornstarch, but will be visually identical to active dose capsules. d-Amphetamine maintenance doses will be administered in an escalating fashion up to the target daily dose (e.g., doses 1-3 = 5 mg, doses 4&5 = 10 mg, doses 6-final = 15 mg for the 30 mg/day dose; doses 1-3 = 5 mg, doses 4&5 = 10, doses 6&7 = 20 mg, doses 8-final = 30 mg for the 60 mg/day dose). Target doses are based on clinical dosing recommendations and a 12-h half-life (Spansule® sustained-release d-amphetamine product information), which will result in the attainment of steady-state blood levels prior to initiating cocaine self-administration sessions. We have safely and successfully used this dose escalation procedure in previous protocols (e.g., Pike et al., 2014).

*Data Analysis.* Self-administration data from the 8 subjects who complete the protocol will be analyzed using two-factor repeated-measures ANOVA with Cocaine Dose (0, 3, 10 and 30 mg/70 kg) and d-Amphetamine SR Maintenance Dose (0, 30 and 60 mg/day) as factors. A significant attenuation in the cocaine self-administration dose-effect curve will be inferred if the main effect of d-Amphetamine or an interaction of the

Cocaine and d-Amphetamine factors attains statistical significance in the ANOVA, and the mean square error term will be used to conduct contrast tests to make appropriate pair-wise comparisons between means. Subjective-effects and physiological data from the Sampling Trial will be analyzed in a similar fashion.

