To minimize the risk associated with intravenous cocaine administration, dosing will occur under the supervision of ACLS-certified medical staff ([name] and CRU nurses). During the medical safety and experimental sessions, heart rate and blood pressure will be recorded prior to cocaine administration and at frequent intervals (i.e., every 2 minutes) afterwards for the duration of the session. Prior to cocaine administration, subjects must have a heart rate of  $< 130$  bpm, systolic blood pressure  $< 165$  mm Hg and diastolic blood pressure  $< 100$  mm Hg. Heart rhythmicity will be recorded continuously via 3-lead telemetry during each experimental session, and will be monitored continuously for a minimum of 15 minutes following each infusion. Subjects who exhibit hypersensitivity (i.e., HR and BP outside of parameters or abnormal ECG) to the cardiovascular effects of cocaine at any point during these studies will not receive further doses, will be followed until symptom resolution, and will be excluded from further research participation. Cardiovascular hypersensitivity is defined as heart rate  $> (220 - \text{subject age}) \times 0.85$ , systolic pressure  $> 180$  mm Hg or diastolic pressure  $> 120$  mm Hg elevated consistently across a five minute period of monitoring (see above). Cardiovascular hypersensitivity also includes prolonged abnormal heart rhythmicity, which is defined as ventricular arrhythmias that occur at a frequency greater than 5 per minute, are multifocal, or occur as couplets

(2 consecutive beats) or salvos (3 or more consecutive beats), and persist for greater than 15 min. Ischemia or other abnormalities as described in the exclusion criteria would also be cause for discharge. A cardiovascular emergency will be managed using UK medical center procedures (i.e., response from a code blue team).

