Subjects will receive intravenous cocaine during maintenance on oral d-amphetamine, which could further increase the risk for adverse cardiovascular events. However, previous clinical research has demonstrated the safety and tolerability of cocaine administration during d-amphetamine maintenance, suggesting that cardiovascular risk in the proposed studies will be minimal. In a study by Greenwald and colleagues (2010), subjects were maintained on d-amphetamine SR at the doses proposed in this application (i.e., 30 and 60 mg/day). d-Amphetamine modestly, but significantly, elevated baseline heart rate and systolic and diastolic blood pressure readings (an increase of approximately 10 bpm, 12 mmHg and 10 mmHg, respectively); however, a bolus dose of 100 mg intranasal cocaine failed to further increase these cardiovascular parameters. In our previous study in which we administered up to 60 mg of intranasal cocaine during maintenance on 30 mg/day d-amphetamine, baseline heart rate and systolic blood pressure were elevated (approximately 6 bpm and 5 mmHg, respectively) and then further increased by cocaine ([name] et al., 2009). However, maximum heart rate did not exceed 95 bpm or 130 mmHg on average following cocaine administration, and no adverse cardiovascular events occurred. In a second study, up to 30 mg of intranasal cocaine was administered during maintenance on 40 mg/day d-amphetamine ([name] et al., 2010). In that study, cocaine significantly increased systolic and diastolic blood pressure, and d-amphetamine maintenance further increased BP, but only by a maximum of about 5 mmHg, and not to a statistically significant degree. Lastly, a review by Herin and colleagues (2010) evaluated the risk profile of d-amphetamine maintenance on an outpatient basis in treatment seekers and found it favorable. The results of several controlled clinical trials incorporating careful monitoring of side effects, including frequently repeated ECGs, indicated that the effects of d-amphetamine maintenance on blood pressure and heart rate were nominal. Similarly, multiple reports from community-based clinics failed to note serious adverse events in diverse populations.

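### A completers-only analysis selects on removals that can depend on treatment, so the d-amphetamine effect can be biased, probably by a small amount and in an unknown direction

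*Protocol*

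**What the plan says.** - **Analysis set.** Protocol section 7, Data Analysis: "Self-administration data from the 8 subjects who complete the protocol will be analyzed using two-factor repeated-measures ANOVA". Subjective and physiological data from the sampling trial are handled in the same way.
- **Recruitment target.** Section 4: "We intend to enroll eighteen (6 female, 12 male) completers into this study". Section 17 also gives 18 subjects.
- **Removal during the study.** Section 10, on subjects whose cardiovascular reaction to cocaine counts as hypersensitivity, with no limit on when it occurs: they "will not receive further doses, will be followed until symptom resolution, and will be excluded from further research participation".
- **Removal before maintenance.** Section 7, on the medical safety session: "subjects exceeding the predetermined cardiovascular parameters will be excluded from further participation".
- **Link to the study drug.** Section 10 says cocaine during d-amphetamine maintenance is a combination "which could further increase the risk for adverse cardiovascular events". Of a cited study at 30 and 60 mg/day it reports that "d-Amphetamine modestly, but significantly, elevated baseline heart rate and systolic and diastolic blood pressure readings", by about 10 bpm, 12 mmHg and 10 mmHg.
- **Order.** Section 7: "The lower active d-amphetamine SR maintenance condition will be tested prior to the higher active condition".
- **Re-admission.** Section 7 allows it for reasons unrelated to study procedures, so it does not bring back cardiovascular removals.

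**The concern.** Completing the protocol is an event that follows treatment. The removal criteria are heart rate, blood pressure and rhythm, and d-amphetamine acts on at least the first two. Subjects removed before or during an active-dose phase never become completers, so the analysed group is chosen partly by its reaction to the drug whose effect is being estimated.

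This matters for the d-amphetamine contrast if cardiovascular reactivity is related to how self-administration changes under d-amphetamine. The design leaves both directions open. If strong cardiovascular reactors are also strong behavioural responders, losing them shrinks the estimated attenuation. But every cocaine choice delivers another infusion, so a subject who keeps choosing cocaine under d-amphetamine is exposed to the removal criteria more often. Losing such subjects would exaggerate the attenuation. For the physiological secondary outcomes, selection acts on the outcome domain itself.

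The rule also discards valid sessions from removed subjects. Removals for a positive drug screen, abstinence symptoms or adverse events lose data in the same way.

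**Working it through.** **1. The plan's own figures.** 4 cocaine doses × 3 maintenance doses = 12 sessions, as stated. The 8 completers cannot be reproduced, because the text at hand gives no effect size, SD, power or dropout. The figure also conflicts with 18.

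**2. Sessions discarded.** With 30 mg before 60 mg there are three sequences: 0-30-60, 30-0-60 and 30-60-0. A subject removed at the start of 60 mg testing has finished 8, 8 or 4 sessions. Taking the sequences as equally likely, the mean is 20/3 = 6.7 of 12. Removal later in that phase can discard up to 11, 11 or 7. For removal in the 30 mg phase, earlier phases contribute 4, 0 or 0 sessions (mean 1.3).

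**3. How often.** Section 7 describes an earlier intravenous cocaine study with 0/22 threshold discharges and 1/22 for rhythm. The exact two-sided 95% upper limits are 15.4% (1 − 0.025^(1/22)) and 22.8%. No d-amphetamine maintenance is described there. With removal share p, reaching 18 completers means replacing 18p/(1−p) subjects: 0.9 at p = 1/22, 2.0 at 10% and 4.5 at 20%.

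**4. Shift in the completers' mean effect.** Assume that reactivity is standard normal, that the top share p is removed, and that reactivity correlates ρ with the individual effect. The shift, in SDs of the individual effect, is ρ·φ(z₁₋ₚ)/(1−p) in size:

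| p | φ(z)/(1−p) | shift at ρ = 0.3 | shift at ρ = 0.5 |
|---|---|---|---|
| 5% | 0.109 | 0.03 | 0.05 |
| 10% | 0.195 | 0.06 | 0.10 |
| 20% | 0.350 | 0.10 | 0.17 |

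The shift is zero at ρ = 0 and changes direction with the sign of ρ. The documents give neither p under d-amphetamine nor ρ.

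**5. What using all the data recovers.** This is a simulation of 3,000 runs per setting. Assumptions: true 60 versus 0 mg contrast −1.00, between-subject SD 1, SD of the individual effect 0.8, residual SD 0.4, and removal in the 30 mg or 60 mg phase. Positive ρ means that stronger reactors attenuate more. The all-data estimate is generalised least squares with known covariance, on phases finished before removal.

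| Completers | Removed at 30 mg / cumulatively by 60 mg | ρ | Completers only | All available data | Bias recovered |
|---|---|---|---|---|---|
| 18 | 3% / 10% | 0 | −0.993 | −0.993 | none present |
| 18 | 3% / 10% | 0.5 | −0.916 | −0.935 | 0.019/0.084 = 23% |
| 18 | 5% / 20% | 0.5 | −0.851 | −0.888 | 0.037/0.149 = 25% |
| 18 | 5% / 20% | −0.5 | −1.144 | −1.107 | 0.037/0.144 = 26% |
| 8 | 5% / 20% | 0.5 | −0.862 | −0.894 | 0.032/0.138 = 23% |

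Step 4 agrees: 0.8 × 0.175 = 0.14 predicts −0.86 at 20% removal and ρ = 0.5. The SD of the estimate falls only slightly, for example from 0.222 to 0.216 (2.7%) at 5%/20% and from 0.222 to 0.220 (0.9%) at 3%/10%, both with 18 completers and ρ = 0.5.

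**The case against.** **Removals may be very few.** Besides the 0/22 and 1/22, section 7 reports no cardiovascular discharges in the ongoing intravenous protocol. Section 10 cites d-amphetamine studies without notable cardiovascular problems. Several filters come before removal: blood pressure screening, a test of every cocaine dose before any d-amphetamine, vital-sign limits before maintenance and cocaine dosing, and repeated readings. This stands, and it is why the size is judged probably small. It does not settle the matter: the intravenous precedents describe no d-amphetamine maintenance, and the d-amphetamine studies whose cocaine route section 10 gives used intranasal cocaine.

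**Replacement protects the sample.** A reader might infer that the trial loses power. The documents do not support that: enrolment runs to a number of completers, so the analysed sample does not shrink. Replacement keeps the number but does not undo the selection.

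**Completers may be the intended target.** For comparing dose-effect curves across species, the effect in people exposed to every dose is a reasonable quantity. The protocol does not state it as the target, however.

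**The analysis plan may say more.** The protocol itself fixes the completers-only set, so this is a stated rule and not a detail left open.

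**Conclusion.** The point holds in a limited form. A stated rule conditions the analysis on an event that can depend on treatment, so the d-amphetamine effect can be biased for the population that starts maintenance. At an assumed 10–20% removal and ρ = 0.5 the shift is about 0.10–0.17 SD of the individual effect; at 5% removal it is about 0.05 SD. Both the removal share and the correlation are assumptions.

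Three stronger readings are tempting but not supported:

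- **That the estimate is biased, or biased in a known direction.** Nothing in the documents links reactivity to behavioural response, and with no link there is no bias.
- **That all reactors leave after a finished 30 mg phase and before 60 mg, so that a model on all data removes most of the bias.** The removal rule acts on reactions to cocaine, so subjects would leave during a phase. With removals placed in both active phases, the model recovers only about a quarter.
- **That exclusions at the medical safety session add to the bias.** They precede any d-amphetamine and yield no self-administration data, so they limit generalisability only.

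**What to change.** - **Primary analysis.** Use a linear mixed model (REML, small-sample degrees of freedom) on all completed experimental sessions of every subject with at least one. Fixed effects: cocaine dose, d-amphetamine dose and their interaction. Random effects: subject and subject-by-d-amphetamine.
- **Sensitivity analysis.** Keep the completers' repeated-measures ANOVA.
- **Reporting.** Give discontinuations by maintenance condition and reason. The model corrects only part of any bias, so readers need these counts.
- **Consistency.** Reconcile the 8 subjects in the Data Analysis sentence with the 18 in sections 4 and 17.

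The cost is analysis wording and slightly more programming. No new data are needed and no safety rule changes. If nobody drops out, the model gives essentially the same contrasts as the planned ANOVA. The downside is reliance on data being missing at random. That is a weaker assumption than a completers-only analysis needs, but it can fail when removal depends on reactivity that the recorded outcomes do not capture. The precision gain is only about 1–3%.

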## 2. OBJECTIVES

The primary objective of this study is to assess self-administration of cocaine vs. a non-drug reinforcer during maintenance on an indirect dopamine agonist, d-amphetamine, in an effort to equilibrate cross-species sensitivity and to provide a comparator for effects of other, non-dopaminergic candidate medications examined in future studies. Multiple d-amphetamine doses will be tested to ensure the functional equivalence of the cocaine and alternative reinforcer magnitudes, which can be further refined, if necessary, prior to testing novel compounds. d-Amphetamine was chosen as a standard because the effects of cocaine have been attributed primarily to blockade of dopamine uptake, and dopaminergic agonists alter laboratory cocaine self-administration in a predictable manner.

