*Subject-Rated Drug-Effect Questionnaires.* Two questionnaires used extensively in human behavioral pharmacology research will be used to measure various aspects of mood and drug effect: 1) Adjective-Rating Scale and 2) Drug-Effect Questionnaire. The subjective-effects measures are described in Appendix A.

*Physiological Indices.* Heart rate, blood pressure and heart rhythmicity (*via* ECG) will be recorded using a Dinamap digital monitor (Critikon, Pro 1000, Tampa, FL). These measures will be measured at least three times in the hour before intravenous drug administration and immediately prior to completion of subject-rated measures for the remainder of session. ECG monitoring will be continuously conducted, and will be printed and read immediately before, and 15 minutes after intravenous drug administration, during the experimental session. Telemetry-certified nurses will interpret the results with instructions to contact Drs. [name], [name] or [name] regarding abnormalities.

*Drug Dose and Administration.* Cocaine and d-amphetamine doses will be administered under double-blind conditions and medical supervision. We currently hold an IND for intranasal cocaine administration and have amended it for IV administration during d-amphetamine maintenance.

Syringes containing the IV cocaine dose for a particular session (i.e., dose in mg/70kg) will be drawn from aseptically prepared stock solutions. Stock solutions are prepared by dissolving cocaine HCl USP (Mallinckrodt, St. Louis, MO) in 0.9% sodium chloride, and filtering the solution through a 0.22  $\mu$ m filter into a sterile, pyrogen-free vial. The doses for administration (3, 10 and 30 mg/70 kg) will be prepared and drawn up into syringes within 24 h of an experimental session and individually labeled for each subject. The 0 mg dose will contain only 0.9% sodium chloride. Each dose will be administered in a standard volume (e.g., 1.0 mL) via a catheter in the non-dominant arm over 30 s. A slow drip of normal saline will be used after initial catheter insertion for the duration of the session to maintain patency and a 10 mL normal saline flush will be administered after each cocaine injection. This method of cocaine preparation has been conducted previously at the UK Investigational Pharmacy, and this procedure for IV administration has been used successfully in our ongoing study.

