##### **Data Monitoring Plan**

Data will be collected using a computerized data collection and management system. This system automates the collection of the self-administration, subjective-effect and physiological data, which ensures the accuracy and completeness of data collection. The data are stored in a unique file on the hard-drive of the computer and are printed at the end of each session. In all instances, the data files do not contain the name of

the subject, but instead, each subject is identified by a unique four-digit number. Data files for experimental tasks and physiological measures from each experimental session will be managed and combined into a single electronic spreadsheet by automated macros. Data for all subjects will then be combined into a single electronic spreadsheet and separated by experimental measure for statistical analysis and graphing.

The primary outcome for these experiments will be the break point and number of self-administered cocaine injections from the concurrent progressive-ratio choice procedure during maintenance on d-amphetamine. The secondary outcomes will be the results from the subjective and physiological measures. Data will be analyzed using ANOVA. The alpha level will be set at 5%.

As noted above, data are collected using an automated computer system, which increases the accuracy and completeness of data collection and ensures the validity and integrity of the data. The quality of manipulated data and data analyses will be monitored by random inspection by the PI and/or Co-Investigators. Interim analysis of the data will be conducted when 50% of the sample is accrued. If statistically significant differences are revealed for all outcome measures, the study will be ended.

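### The written criterion for attenuation is met by an increase, or by a change at saline alone, because it rests on two direction-free F-tests and does not depend on the planned contrasts

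*Protocol*

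**What the plan says.** Section 7 of the protocol (Data Analysis) specifies a two-factor repeated-measures ANOVA with "Cocaine Dose (0, 3, 10 and 30 mg/70 kg) and d-Amphetamine SR Maintenance Dose (0, 30 and 60 mg/day) as factors". The decision rule follows: "A significant attenuation in the cocaine self-administration dose-effect curve will be inferred if the main effect of d-Amphetamine or an interaction" between the two factors reaches significance. The same sentence then turns to follow-up tests: "the mean square error term will be used to conduct contrast tests to make appropriate pair-wise comparisons between means". It does not say which contrasts these are, or what they must show before attenuation is inferred.

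Under Drug Dose and Administration, the same section says of the lowest cocaine level: "The 0 mg dose will contain only 0.9% sodium chloride". The Data Monitoring Plan (section 17) states "The alpha level will be set at 5" per cent, and names break point and number of cocaine injections as the primary outcome. Section 2 explains how the result will be used: "to provide a comparator for effects of other, non-dopaminergic candidate medications examined in future studies". No section adds a requirement on direction or on cocaine dose.

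**The concern.** Attenuation is a directional conclusion about cocaine-maintained responding. The written rule reaches it from two tests that measure only whether means differ. The main effect of maintenance pools over all four cocaine levels, including saline. The interaction responds to any non-parallel pattern. Three kinds of result can therefore satisfy the rule without any attenuation: an overall increase, a change confined to saline, and a mixed pattern such as a rise at one low cocaine dose.

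This is the only stated criterion for the main conclusion, and d-amphetamine is meant to be the standard against which later medications are judged. A mislabelled result here would carry into those comparisons.

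**Working it through.** **Inputs from the protocol.** There are 3 maintenance levels and 4 cocaine levels, and alpha is 5%. The number of completers is 8 in Data Analysis and 18 in section 4 ("We intend to enroll eighteen (6 female, 12 male) completers into this study"). That conflict is a separate matter, so both values are used.

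**Assumptions.** The protocol gives no effect sizes or variances. Effects are in residual SD units: residual SD 1, subject SD 1, subject-by-cocaine SD 0.5, subject-by-drug SD 0, 0.5 or 1. Triples below follow that last order. A pair such as 0.5 and 1 SD means the shift at 30 and at 60 mg/day.

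**Degrees of freedom.** Main effect: 3 − 1 = 2, with error 2(n − 1) = 14 or 34. Interaction: 2 × 3 = 6, with error 6(n − 1) = 42 or 102.

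**Step 1: no sign.** The main-effect noncentrality is λ = 4n Σ(mean_j − grand mean)², which is unchanged if every shift is reversed. For shifts 0, 0.5, 1 at all cocaine doses, with subject-by-drug SD 0, the deviations are −0.5, 0, 0.5 and their squares sum to 0.5.
- n = 8: λ = 4 × 8 × 0.5 = 16, and the test is significant with probability 0.903.
- n = 18: λ = 4 × 18 × 0.5 = 36, probability above 0.999.

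The same values hold for an increase and for a decrease.

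**Step 2: saline alone is enough.** Take shifts 0, 0.75, 1.5 at 0 mg cocaine only, again with subject-by-drug SD 0.
- Row means are 0, 0.1875, 0.375, so the sum of squared deviations is 2 × 0.1875² = 0.0703.
- Main effect: λ = 4 × 8 × 0.0703 = 2.25, probability 0.209 (n = 8).
- Interaction: the saline column contributes 2 × 0.75² = 1.125. Removing the main-effect part, 4 × 0.0703 = 0.281, leaves 0.844. Then λ = 8 × 0.844 = 6.75, probability 0.393.
- At n = 18 the two probabilities are 0.472 and 0.822.

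By simulation, at least one test is significant in 52% (n = 8) and 91% (n = 18) of trials.

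**Step 3: the rule with and without a contrast condition.** Each F-test was simulated against its own subject-by-effect error term. The last column adds one requirement: at least one unadjusted paired contrast (30 or 60 against 0 mg/day, at 3, 10 or 30 mg/70 kg cocaine) is significant at two-sided 5% and negative.

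| True pattern | n | Rule as written | With contrast condition |
|---|---|---|---|
| No effect | 8, 18 | 9.4–10.0% | about 3–4% |
| Saline rise, 0.5 and 1 SD | 8 | 28/25/23% | about 5–6% |
| | 18 | 56/50/47% | about 8–10% |
| Saline rise, 1 and 2 SD | 8 | 78/73/70% | about 10–13% |
| | 18 | 100/99/98% | about 10–13% |
| Rise at 3 mg/70 kg only, 0.5 and 1 SD | 8 | 27/25/23% | about 4% |
| | 18 | 56/50/48% | about 6–7% |
| Decrease at all active doses, 0.5 and 1 SD | 8 | 73/50/34% | 67/46/27% |
| | 18 | 99/87/65% | 99/86/59% |
| Decrease at 10 mg/70 kg only, 0.5 and 1 SD | 8 | 28/24/22% | 22/17/13% |

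Separate simulation runs differ by one or two percentage points. In the last three rows a claim is correct, so those figures are power.

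**Step 4: the error term.** The protocol refers to the mean square error without saying which one, and a two-factor within-subject ANOVA has several. The three-way interaction mean square omits subject-by-drug variance. With Holm-adjusted contrasts, after the larger saline rise at n = 8, that term gives false attenuation in 2.5/4.3/10.9% of runs. The paired difference gives 2.4/2.2/2.1%.

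**The case against.** The strongest reply is that the defect needs a literal reading of half a sentence. Attenuation means a decrease, and an omnibus test followed by contrasts is the usual sequence. A reader might infer from the 91–100% figures for an overall increase (subject-by-drug SD 0) that the trial would probably report an increase as attenuation. The documents do not support that, because it would need an analyst who ignored the means and the planned contrasts. The 70–100% figures for saline likewise describe the criterion as worded, not the likely conduct of the analysis. This part of the objection stands and limits the weight of the point.

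It is also fair that the response requirements were chosen partly to keep placebo self-administration low, so a large saline rise is not expected. For an assumed small rise of 0.15 and 0.3 SD, the written rule is met in 11–12% (n = 8) and 12–14% (n = 18) of trials, close to the no-effect rate of about 10%. Larger rises trigger it often, but those sizes are assumptions.

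Finally, named contrasts, their multiplicity adjustment and the exact error term may properly sit in a statistical analysis plan that is not shown. That is accepted for the adjustment. It does not answer the main point: the protocol itself states the decision rule, and the clause on contrasts describes a follow-up procedure with no result that must hold.

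**Conclusion.** The point holds and should be fixed, with modest practical impact. That the criterion is blind to direction, and can be met by saline alone, follows from the wording at any effect size. The percentages depend on the assumed effects and variances. The realistic risk is a saline-driven or mixed-pattern interaction being labelled attenuation because the written condition is met.

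Two stronger readings are not supported. Including saline in the ANOVA is not an error in itself; the fault is that a saline-only change is enough for the claim. And the roughly 10% chance of meeting the either/or rule with no effect is not raised as a separate alpha violation: the protocol states 5% without saying that it covers the two tests jointly.

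**What to change.** Keep the two F-tests as the gate and add, for example:

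> Attenuation will be inferred only if, in addition, at least one planned contrast of active versus 0 mg/day d-amphetamine maintenance at an active cocaine dose (3, 10 or 30 mg/70 kg) is statistically significant and shows a decrease. A change at 0 mg cocaine alone will be reported separately and will not count as attenuation.

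State that the contrast error term includes subject-by-d-amphetamine variance; the paired difference between the two cells is one way.

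The cost is two or three sentences, with no new data, plus the loss of power shown above. The loss is small for a broad decrease (at most about 7 percentage points) and larger for an effect at a single cocaine dose (6 to 9 points at n = 8).

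Two stricter options lower false claims further but trade away power. Holm adjustment over the six contrasts cuts power for the broad decrease to 36/24/13% at n = 8. A single contrast averaged over the active cocaine doses, behind the same gate, gives 64/38/17% there but only 8/5/4% for an effect at 10 mg/70 kg alone. Neither is needed to correct the rule, and the choice is the sponsor's.
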